At each therapy session, participants will complete the PCL-5 (Weathers et al., 2013) and TLFB (Sobell & Sobell, 1996) in order to assess self-reported PTSD symptomatology, opioid use, illicit and licit non-opioid drug use, alcohol use, and access to support services. Therapy sessions may be conducted in-person or remotely via Zoom platform. At 4-, 8-, and 12-weeks post-randomization, all participants will complete follow-up assessments consisting of an abbreviated version of the intake and participants randomized to receive PET will also complete the Working Alliance Inventory Client Form (WAI; Horvath & Greenberg, 1989). A participant satisfaction questionnaire will also be administered at Week 12. Follow-up assessment visits will be conducted in-person at our clinic at UHC. However, study measures may also be administered remotely via phone or Zoom platform. Furthermore, if a participant is at high-risk and/or currently experiencing COVID-19 symptoms, urine collection may be excused and study measures can be administered remotely via phone or Zoom platform. Regardless of experimental group, all participants will receive \$60 for completing the initial intake assessment and \$150 for completing follow-up assessments at 4-, 8-, and 12-weeks post-randomization.

For research involving survey, questionnaires, etc.: Describe the setting and the mode of administering the instrument and the provisions for maintaining privacy and confidentiality. Include the duration, intervals of administration, and overall length of participation.

Not applicable

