Study procedures will be conducted in-person at UVM Substance Abuse Treatment Center or remotely via phone or UVM's institutionally supported Zoom platform. The intake assessment will include the LEC-5 (Weathers et al., 2013), the CAPS-5 (Weathers et al., 2013), PCL-5 (Weathers et al., 2013), Mini International Neuropsychiatric Interview (MINI; Sheehan et al., 1998), Addiction Severity Index (ASI; McLellan et al., 1985), Beck Depression Inventory-II (BDI-II; Beck et al., 1996), Beck Anxiety Inventory (Beck & Steer, 1993), Patient Health Questionnaire - 9 (PHQ-9; Kroenke et al., 2001), Generalized Anxiety Disorder 7-Item Scale (GAD-7; Spitzer et al., 2006), Brief Pain Inventory – Short Form (BPI-SF; Cleeland et al., 1994), The Monetary Choice Questionnaire (MCQ; Kirby et al., 1999), Insomnia Severity Index (ISI; Morin et al., 2011), Credibility/Expectancy Questionnaire (Devilly & Borkovec, 2000), a Demographic and Drug History Questionnaire developed by our group, and a Time Line Follow-Back (TLFB; Sobell & Sobell, 1996) of opioid use, illicit and licit non-opioid drug use, alcohol use, and access to support services. Participants will also provide a urine specimen for immediate onsite testing for opioids (e.g., heroin, methadone, buprenorphine, oxycodone, fentanyl) as well as other, non-opioid drugs (e.g., cocaine, amphetamines, benzodiazepines). Finally, if impairment is suspected, participants may be asked to provide a breath sample. Participants randomized to the OAT+PET and OAT+PET⁺ conditions will complete therapy sessions with research clinicians once per week while receiving PET as described above. Therapy sessions may be conducted in-person or remotely via Zoom platform. At each therapy session, OAT+PET and OAT+PET⁺ participants will complete the PCL-5 (Weathers et al., 2013) and Time Line Follow-Back (TLFB; Sobell & Sobell, 1996) in order to assess self-reported PTSD symptomatology, opioid use, illicit and licit non-opioid drug use, alcohol use, and access to support services. Participants randomized to receive OAT as usual will continue to receive standard buprenorphine or methadone maintenance from their current treatment provider, though all participants will complete follow-up assessments at 4-, 8-, and 12-weeks post-randomization. A participant satisfaction questionnaire will also be administered at Week 12. Follow-up assessment visits will be conducted in-person at our clinic at UHC. However, study measures may also be administered remotely via phone or Zoom platform. Furthermore, if a participant is at high-risk and/or currently experiencing COVID-19 symptoms, urine collection may be excused and study measures can be administered remotely via phone or Zoom platform. Follow-up assessments will consist of an abbreviated version of the intake and participants randomized to receive PET will also complete the Working Alliance Inventory Client Form (WAI; Horvath & Greenberg, 1989).

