Statistical Considerations: Delineate the precise outcomes to be measured and analyzed. Describe how these results will be measured and statistically analyzed. Delineate methods used to estimate the required number of subjects. Describe power calculations if the study involves comparisons. Perform this analysis on each of the primary and secondary objectives, if possible.

Statistical Methods

The three experimental groups will be compared on baseline characteristics using analyses of variance for continuous variables and chi-square tests for categorical variables. If characteristics differ significantly and are predictive of outcome, they will be considered as potential covariates in subsequent analyses. Primary analyses will include all randomized subjects independent of early dropout, consistent with an intent-to-treat approach (Armitage, 1983). For our primary outcome of PTSD severity (CAPS-5) and secondary outcomes of psychiatric distress (BDI, BAI) and drug use (e.g., ASI subscales), mixed-models repeated measures analyses with subjects as random effects (SAS, PROC MIXED) will be used to compare the three groups across Week 4, 8, and 12 assessments. Fixed factors will include treatment condition and the within-subject factor, assessment timepoint, along with their interaction. Linear contrasts will be used to compare experimental conditions on changes from baseline to post treatment assessments, partial F-tests will be used to examine simple effects and pairwise comparisons will be based on Fisher's Protected LSD.

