Adverse Event, Unanticipated Problem (UAP), Reportable New Information (RNI): Describe how events and UAPs will be evaluated and reported to the IRB. All protocols should specify that, in the absence of more stringent reporting requirements, the guidelines established in the "Adverse Event and Unanticipated Problems Reporting Policy" will be followed. The UVM/UVM Medical Center process for review of adverse events and UAPs to subjects or others should be included in the DSMP.

AEs and SAEs will be assessed at each clinic visit by a trained RA or research therapist. Any SAE will be brought to the attention of the PI as soon as possible and not longer than 24 hrs. Any SAE, whether or not related to study intervention, will be reported to the IRB's CHRBSS using the UVM Adverse Event Reporting Document within 5 days of the event. The CHRBSS will determine whether additional reporting requirements are needed. Any SAEs will also be summarized in the yearly IRB continuing review, including a review of frequency and severity.

Withdrawal Procedures: Define the precise criteria for withdrawing subjects from the study. Include a description of study requirements for when a subject withdraws him or herself from the study (if applicable).

OAT+PET and OAT+PET⁺ participants who miss four consecutive weeks of treatment no longer be eligible to continue in PET but will be eligible to complete follow-up assessments. Furthermore, continued enrollment in standard buprenorphine or methadone maintenance treatment is necessary for patients to continue in PET. Patients who drop out of buprenorphine or methadone maintenance treatment will no longer be eligible for the study and their participation will be terminated. Patients are free not to participate in this study or to withdraw from it at any time. If they decide not to participate in the study, we will be glad to discuss with them other clinically appropriate treatment referrals for PTSD that may be available in Vermont. If patients decide not to participate in this study or to withdraw from this study, their decision will not prejudice their future medical care.

Sources of Materials: Identify sources of research material obtained from individually identifiable human subjects in the form of specimens, records or data. Indicate whether the material or data will be obtained specifically for research purposes or whether use will be made of existing specimens, records or data.

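### Leaving opioid agonist treatment ends study participation, so outcome follow-up stops at a post-randomisation event and the missing-data assumption this forces is neither stated nor tested

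*Combined protocol and SAP*

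**What the plan says.** Withdrawal Procedures contains three separate rules.

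1. PET participants who miss four consecutive weeks stop PET but "will be eligible to complete follow-up assessments".
2. For PET itself, "continued enrollment in standard buprenorphine or methadone maintenance treatment is necessary for patients to continue in PET".
3. "Patients who drop out of buprenorphine or methadone maintenance treatment will no longer be eligible for the study and their participation will be terminated".

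The section on screening and on-study procedures sets the visit schedule: "At 4-, 8-, and 12-weeks post-randomization, all participants will complete follow-up assessments consisting of an abbreviated version of the intake". The later section on study questionnaires and their setting repeats it, "though all participants will complete follow-up assessments at 4-, 8-, and 12-weeks post-randomization". The procedures section also provides that "study measures may also be administered remotely via phone or Zoom platform", and sets a $150 payment "for completing follow-up assessments at 4-, 8-, and 12-weeks post-randomization".

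Statistical Methods states: "Primary analyses will include all randomized subjects independent of early dropout, consistent with an intent-to-treat approach". The primary outcome, CAPS-5, is analysed by a repeated-measures mixed model over Weeks 4, 8 and 12, with contrasts on change from baseline. OAT retention and illicit-opioid abstinence are exploratory outcomes at the same visits, analysed by GEE. No missing-data assumption, imputation rule or sensitivity analysis is given, and Sample Size Justification states no allowance for attrition.

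**The concern.** Rule 3 does not mention assessments, so its scope has to be inferred. If it ended only PET, it would repeat rule 2. If assessments were meant to continue, one would expect the exception written into rule 1. It speaks of the study, not of PET, and of patients generally, not of the PET arms. The natural reading is that outcome assessment ends too, in all three arms, and nothing elsewhere in the document restores it. A reading confined to the PET arms would be worse, because follow-up would then differ by arm.

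The trigger for losing data is therefore a post-randomisation event that is itself a trial outcome and could be affected by PET or by the incentives. If leavers' later CAPS-5 differs from what their earlier visits predict, the primary contrast is biased. Neither the size nor the direction could be checked, because the data that would show it were never collected. Equal leaving rates across arms do not remove the problem if leavers fare differently by arm.

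**Working it through.** **Inputs from the documents.** 45 per arm; 80% power; alpha .05 (two-sided assumed); a difference of 8 CAPS-5 points in change from baseline to Week 12 (Sample Size Justification).

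**Not in the documents.** The SD of change, the OAT-leaving rate and leavers' CAPS-5 course. The SD is back-solved; the other two are assumed over a range.

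**Step 1: the plan's own figure.** The 80% cannot be reproduced without an SD, so I solved for the SD that gives it. For a two-sample t-test (noncentral t, 88 df) the result is SD = 13.40. The standard error of the contrast is 13.40 × √(2/45) = 2.82 points. This takes the 80% to refer to 45 analysed per arm.

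**Step 2: power if a share d of each arm lacks Week 12**, using n = 45(1 − d) and the same SD.

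| d | n per arm | Power for 8 points | Difference detectable at 80% |
|---|---|---|---|
| 0 | 45 | .800 | 8.00 |
| 5% | 42.75 | .779 | 8.21 |
| 10% | 40.5 | .756 | 8.44 |
| 20% | 36 | .705 | 8.97 |

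The mixed model recovers part of this loss from earlier visits, so under the Step 1 assumption these are worst cases. They apply to any Week 12 loss, not only to loss through this rule.

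**Step 3: participants with no post-baseline CAPS-5.** If leaving is spread evenly over the three intervals between visits, one third of leavers go before Week 4: 45 × .10 / 3 = 1.5 per arm at 10% leaving, and 45 × .20 / 3 = 3 at 20%.

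**Step 4: bias when the model assumes missing at random.** Let p be the share leaving and w the number of points by which leavers' Week 12 CAPS-5 is worse than their earlier visits predict. Bias in favour of arm A over arm B = pA·wA − pB·wB.

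| pA, pB | wA, wB | Calculation | Bias (points) | Simulated |
|---|---|---|---|---|
| 20%, 10% | 5, 5 | .20×5 − .10×5 | 0.5 | 0.49 |
| 20%, 10% | 12, 12 | .20×12 − .10×12 | 1.2 | 1.20 |
| 15%, 15% | equal | difference cancels | 0 | about 0 |
| 15%, 15% | 12, 5 | .15×12 − .15×5 | 1.05 | about 1.06 |
| 20%, 10% | 12, 5 | .20×12 − .10×5 | 1.9 | about 1.9 |
| 20%, 10% | 5, 12 | .20×5 − .10×12 | −0.2 | −0.20 |

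The last column simulates 400,000 per arm, with an assumed within-person correlation of .5, the first missed visit uniform over Weeks 4, 8 and 12, and arm-specific sequential regression for the missing values. It confirms that conditioning on earlier visits does not remove a departure of this kind.

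**The case against.** The strongest reply is that this is one ambiguous sentence and not a flaw in the analysis. A visit schedule for all participants is ordinarily read as subject to withdrawal rules. The mixed model keeps every observed visit, so analysis by allocation survives. A while-on-OAT question would fit an objective framed as the effect of PET beyond OAT. The stable-dose entry requirement may keep leaving rare.

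Much of this is fair. The schedule and the withdrawal rule conflict only if the first is not subject to the second, and the plan does not say which holds. The rule undermines the intent-to-treat aim without strictly contradicting it. The need for a missing-data assumption would exist without this rule. What stands is that the rule adds avoidable loss, tied to an outcome, and that a while-on-OAT question is stated nowhere and would have to be squared with the intent-to-treat statement.

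On size, the leaving rates and the 5 to 12 point shifts have no source in the documents, and every bias shown is below the standard error. The power figures are also conditional. If 20% attrition were already built into the 80%, the implied SD would be about 12.1 (normal approximation), and losing 20% would leave power at 80%. These points limit severity. They do not make the bias checkable.

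Two points of scope also stand. Protection Against Risk withdraws participants for substantial emotional reactions or for danger to self or others, which may leave the same kind of gap. Remote assessment also cannot supply a urine specimen, so it helps CAPS-5 and self-report more than verified abstinence.

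**Conclusion.** The concern holds, as something that should be fixed at low cost; it does not invalidate the design. Confidence is medium, because the rule's reach over assessments is inferred from its neighbouring sentences. Followed as naturally read, the plan stops measuring the primary outcome after a post-randomisation event that is itself an exploratory outcome, and Week 12 then rests on an unstated, untested missing-at-random assumption.

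Under the assumed inputs the effect is modest: at worst 2 to 9 percentage points of power at 5% to 20% loss, and bias between −0.2 and 1.9 points against a target difference of 8. The direction is not fixed. A systematic error of this kind is not reflected in the standard error and cannot be examined once follow-up has been forgone.

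**What to change.** - Amend Withdrawal Procedures so that leaving OAT does not by itself end research outcome assessment. With the participant's agreement, continue the Week 4, 8 and 12 assessments, remotely where needed, and include those data in the CAPS-5 model.
- State the missing-at-random assumption. Add one sensitivity analysis that shifts leavers' unobserved CAPS-5 values over a stated range, with the shift allowed to differ by arm. It would sensibly cover the other withdrawal routes too.
- Count leavers as not retained in OAT, with all randomised as the denominator. Analyse abstinence over all randomised, with a sensitivity analysis for missing values, and say how it is handled when no urine specimen is available.
- If a while-on-OAT question is intended instead, state it and reconcile it with the intent-to-treat statement.

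No view is taken on the clinical rules for PET eligibility or safety withdrawal. The withdrawal, follow-up and statistical sections need reconciling on data collection and analysis only.

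**Cost.** A short protocol and consent amendment, plus effort to reach people who have left OAT. The visits, remote options and payments are those already planned for everyone. Some leavers will decline or be unreachable, so the sensitivity analysis is still needed.
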